The adverse effects of excess weight and weight gain on prognosis in breast cancer patients are thought to be largely mediated by reduced insulin sensitivity, impaired glucose tolerance and hyperinsulinemia (20). Reduced insulin sensitivity and impaired glucose tolerance have been reported in 50% of patients with metastatic breast cancer (MBC) in two recent cohorts where it was linked to poorer response (7) (21). In women receiving paclitaxel chemotherapy for MBC, Stebbing et al reported clinical benefit rates of 40.5% vs 65.8% in women with and without impaired glucose tolerance respectively (7). In a multivariate analysis the odds ratio (OR) of disease progression per unit increase in fasting glucose was 5.47 (95% CI 2.05–14.60). Similarly, Gennari et al reported a median progression free survival (PFS) of 8 months (IQR 2-17) in MBC patients with insulin resitance (HOMA index >2.5) compared with 14 months (IQR 8-18) in patients with normal insulin sensitivity (HOMA index <2.5) (n = 87 standard). The multivariate hazard ratio of disease progression was 2.28 (95% CI 1.06–4.89) in patients with insulin resistance (21). Insulin resistance is common amongst these patients and can be further increased during chemotherapy because of weight gain, direct cellular effects of chemotherapy and the use of corticosteroids as anti-emetics and to prevent reactions to the taxanes (20, 22).

Energy restriction is thought to act partly down stream of insulin through inhibition of the mTOR signal transduction pathway. The likely benefits of energy restriction in patients with MBC are suggested by beneficial effects of mTOR inhibitors such as everolimus (Ev) which has been shown to improve PFS when given in combination with endocrine therapy (23, 24) and chemotherapy (23). However, drugs such as Ev are associated with a significant increase in toxicity. Our hypothesis is that weight loss and energy restriction in advanced disease will phenocopy mTOR inhibitors in extending PFS but, in contrast to pharmacological mTOR inhibition, will reduce toxicity and improve quality of life. It is also worth noting that energy restriction mimetics such as metformin are also being tested in MBC (25-27).

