Once the proforma has been received, the B-AHEAD 3 research team at MFT will then contact the patient to arrange a baseline appointment. The baseline appointment should ideally occur at least 2 days before commencing the planned course of chemotherapy. However potential participants will be informed that they can join the study at any time up to Day 15 of their chemotherapy cycle.

Using the initial approach we have successfully recruited 47 - 48% of eligible chemotherapy patients from the Greater Manchester NIHR Clinical Research Network into our previous randomised diet and

exercise B-AHEAD 1 and B-AHEAD 2 studies in the same hospitals outlined above. Assuming a conservative 35% uptake amongst advanced breast cancer patients we anticipate recruitment should be completed within 15 months.

Ideally baseline assessments will take place at The Nightingale Centre. It is recognised that between consent and undergoing the baseline assessments at The Nightingale Centre, participants have time to change their mind about joining the study so we are not concerned that not having this consent visit would make women join the study before they have had time to consider it.

As recruitment has been slower than anticipated, participants can now have their baseline assessments and blood samples in their recruiting hospital. Blood samples will only be taken if the centre has -80°C storage facilities or if the samples can be transferred to MFT or another centre with -80°C storage facilities within an acceptable time frame.

If baseline assessments are taking place at the recruiting hospital, there must be at least 24 hours between the participant receiving the PIS and the assessments taking place in order to allow the participant time to consider the study.

Posters and leaflets to raise awareness of the study will be displayed in patient areas.

6.4 **Procedures for during and end of the study**

The energy restriction and exercise interventions will continue until the first disease progression after commencement of study chemotherapy, even if chemotherapy had been stopped due to toxicity. Approximately 30% of patients have an objective response, whilst 20% have stable disease. The average chemotherapy period of treatment is projected to be 5.4 months. The longest treatment period is predicted to be two years. We plan to censor patients in the study once the final recruited patient has been in the trial for 12 months.

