We plan to assess the effects of the intervention vs. control on insulin resistance which we hypothesise to be an important mediating variable which could predict success of the IER and resistance exercise intervention. We will assess the effects of the interventions on insulin resistance using HOMA (Homeostasis model assessment) from fasting insulin and glucose measurements (81).

We are assessing whether baseline proteomic signal can predict response and non-response to chemotherapy in **all trial participants** (see above). Patients in this sub-study will have repeat blood tests at cycle 3 or 4 so we can assess the effect of the intervention on the proteomic plasma signature to obtain a comprehensive assessment of any changes in known host proteins of interest, e.g. IGF-1, HIF-1 leptin, adiponectin, steroid hormones, cytokines, vascular regulators, and inflammation related molecules as well as novel biomarkers.

The benefits of IER are due to both acute metabolic effects which occur during the 2 days of restriction and more chronic beneficial effects throughout the subsequent non fasting days. Typically 3 months of IER reduces insulin by 25%, with a further acute 25% decrease during the 2 days of restriction (44, 92). A true evaluation of the metabolic effects of IER thus requires assessment of during both the fasting and non-fasting days.

We therefore plan to assess HOMA insulin resistance and protein blood-based biomarkers at:

1. Baseline (before starting chemotherapy and the diet/and or resistance exercise)

2. On the day of the third or fourth chemotherapy cycle just after the 2 fasting days in the IER group⁺.

3. Two days before the third or fourth chemotherapy cycle, i.e. five days after completion of fasting days in the IER group to assess the durability of the effects of IER on the five normal eating days[†].

[†] We will take two fasting blood samples in the exercise only control group. Timing these samples around diet days is not vital in this group so the timing of these samples can be flexible. For premenopausal women we will record the day of menstrual cycle as this can have a small effect on measures of insulin resistance (93).

Exploratory objectives

1a. Is there a different proteomic signal at baseline between responders and non-responders?

1b. Is there a difference in insulin resistance at baseline between responders and non-responders?

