16.4 Serum blood tests

Fasting glucose and insulin will be assessed where possible in all participants attending baseline appointment either at MFT or their recruiting centre, and repeated at the start of cycle 3 or 4 for patients on sub-study 1 only. Glucose results will be fed back to the patient's oncologist during the study if outside of the normal range. Other blood test results will not be available until after the end of the study so there are no plans to feed these back to the medical team. Baseline and sub study blood samples will only be taken in centres which have -80°C storage facilities or if the samples can be transferred to MFT or another centre with -80°C storage facilities within an acceptable time frame.

Phlebotomy will be undertaken on the non-operated arm wherever possible to minimise the risk of lymphoedema. The study is designed so participants will have their trial blood samples collected at the time of routine chemotherapy blood tests wherever possible to minimise venepuncture.

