Appendix 5: Serum and plasma collection, handling and storage

Sample collection

Baseline blood samples will be collected at MFT or chemotherapy centres before initiating the diet and exercise programmes. The two sub-study 1 samples will be collected in the chemotherapy centres two days before chemotherapy (this may coincide with the time of normal pre-treatment blood tests for women on paclitaxel) and on the day of chemotherapy treatment. Women will be asked to fast for 12 hours and they will receive a complimentary light breakfast immediately after blood collection if at MFT. Samples will be spun, aliquoted and processed and stored at -80°C at MFT or in the chemotherapy centres.

Biohazards and safety requirements to be met with the handling of all human blood samples; the procurement, handling and storage of blood specimens will be undertaken by personnel who have received training in the risks associated and safety requirements. Standard operating procedures are in place to comply with good clinical practice and good laboratory practice.

Insulin serum SST (BD Vacutainer: orange top)

Samples should be centrifuged as soon as possible after collection to separate the serum from the cells. Serum can then be stored for 24 hrs at 2-8°C or 1 month at -15 to -25°C before storing at -80°C. Insulin samples will be stored at -80°C at the site of collection then transported for analysis to MFT. Insulin will be measured by clinical biochemistry at MFT using a commercially available chemoluminescence immunoassay. All assays will be batched and performed on stored serum (-80°C) upon completion of the study to reduce inter-batch variation.

Glucose fluoride (BD Vacutainer: grey top)

Glucose will be assessed using a Hexokinase/glucose-6-phosphate dehydrogenase method. This will be analysed in the recruiting centres or at MFT as soon as possible or stored at 4°C. Freezing and long term storage of these samples is not recommended.

Plasma collection and storage for proteomic analysis (BD Vacutainer: purple top)

Sample for proteomic analysis will be collected in EDTA tubes (10ml tube or 3 x 4ml tube or equivalent). After collection the tube should be inverted 8-10 times and spun within 30 minutes. Centrifugation will be for 10 minutes at 2000g with plasma removed from the upper layer. After preparation the sample

B-AHEAD 3 | Protocol | v7.0 | 02/10/18 | Page 47

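### Sub-study 1 fixes diet-arm blood samples relative to the chemotherapy dose but leaves control timing open, so the between-arm change in HOMA and proteome can be biased; separately, the pre-chemotherapy baseline conflicts with Day 15 entry

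*Protocol*

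**What the plan says.** **Follow-up samples.** Protocol section 8.1.3 (Sub-study 1) sets two follow-up times for HOMA and the protein biomarkers. One is "On the day of the third or fourth chemotherapy cycle just after the 2 fasting days in the IER group". The other is "Two days before the third or fourth chemotherapy cycle, i.e. five days after completion of fasting days in the IER group". A footnote then releases the control arm: "Timing these samples around diet days is not vital in this group so the timing of these samples can be flexible". Appendix 5 makes no distinction by arm: "The two sub-study 1 samples will be collected in the chemotherapy centres two days before chemotherapy", and again on the treatment day. Section 16.4 has the tests "repeated at the start of cycle 3 or 4 for patients on sub-study 1 only", and Appendix 7 places them twice around cycle 3 or 4 in a table headed for both arms.

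**Drug effects.** Section 2.2 says that insulin resistance can rise during chemotherapy through weight gain, direct cellular effects of the drugs, and "the use of corticosteroids as anti-emetics and to prevent reactions to the taxanes".

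**Baseline.** Section 8.1.3 defines it as "Baseline (before starting chemotherapy and the diet/and or resistance exercise"), and section 2.6 likewise puts the first proteomic sample before chemotherapy. Section 6.3 tells women that "they can join the study at any time up to Day 15 of their chemotherapy cycle". The exclusion in section 6.2 removes only those beyond Day 15, and section 7.1.1 makes provision for women already on treatment. Appendix 5 asks only that the baseline sample precede the diet and exercise programmes.

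**The concern.** The reason given for freeing control timing concerns diet days alone. Control women receive the same chemotherapy and supportive steroids, and on the protocol's own account these can move the quantity being measured. If one arm is sampled at a fixed point relative to the dose and the other is not, the difference in change between arms mixes the effect of the diet with the effect of time since treatment. Change in proteome and change in HOMA are secondary objectives 8 and 9, and section 8.1.3 presents insulin resistance as a hypothesised mediator of the intervention. An analysis plan cannot fully repair samples that were not taken comparably.

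The baseline conflict is a separate matter. Some values called baseline may be drawn after the first dose. They then serve as the reference for change and as predictors of response.

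**Working it through.** **1. The passages side by side (follow-up samples)**

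| Place | Diet arm | Control arm |
|---|---|---|
| 8.1.3 | two days before, and on the day of, cycle 3 or 4 | open |
| Appendix 5 | two days before, and on the day | same (no exception) |
| 16.4 | start of cycle 3 or 4 | same |
| Appendix 7 | twice around cycle 3 or 4 | same |

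Control samples are therefore held near cycle 3 or 4, but under 8.1.3 not to a day relative to the dose. Sites following 8.1.3 and sites following Appendix 5 could sample controls differently.

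**2. The plan's own effect figures.** Section 8.1.3 expects insulin to fall by 25% after three months of the diet, with a further acute 25% on restricted days. Read as successive reductions this is 0.75 × 0.75 = 0.56 of the starting value. The protocol states no sample size for sub-study 1 and no size for a steroid or chemotherapy effect, so the shifts below are assumptions.

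**3. Bias from control timing, no true diet effect.** Let open timing raise HOMA by a proportion x in a share f of controls. On the log scale the spurious diet/control ratio is (1 + x)^(−f).

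| x | f = 1 | f = 0.5 |
|---|---|---|
| 10% | 1/1.10 = 0.91 (9% lower) | 1.10^(−0.5) = 0.95 (5% lower) |
| 20% | 1/1.20 = 0.83 (17% lower) | 1.20^(−0.5) = 0.91 (9% lower) |
| 50% | 1/1.50 = 0.67 (33% lower) | 1.50^(−0.5) = 0.82 (18% lower) |

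To imitate the 25% lasting fall by timing alone, every control would need x = 1/0.75 − 1 = 33%. That equates HOMA with insulin, which holds only if glucose is unchanged.

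**4. The bias can reverse.** If control samples fall further from steroid exposure than the diet arm's, and control HOMA is 20% lower as a result, a true ratio of 0.75 appears as 0.75/0.80 = 0.94. Most of the effect is hidden.

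**5. Late baseline.** Let a share q of women in each arm have baseline HOMA raised by s because chemotherapy has begun. Appendix 5 puts the sample before the interventions, and its timing does not depend on arm, so q and s are the same in both arms in expectation.

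- Between arms: the shift −q·ln(1 + s) cancels. Simulated mean log differences (20,000 replicates; q = 0.3 or 0.5, s = 20% or 50%) were at most 0.0013 in size.
- Within an arm: change is biased by the ratio (1 + s)^(−q), from 1.20^(−0.3) = 0.95 to 1.50^(−0.5) = 0.82.
- Precision: assume a log-SD of 0.4 and 20 women per arm. The standard error without late baselines is 0.4 × √(2/20) = 0.126. With q = 0.5 and s = 50%, the variance per woman is 0.16 + 0.25 × (ln 1.5)² = 0.201, giving √0.201 × √(2/20) = 0.142, about 12% more. Simulation gave 0.127 and 0.143, about 13%.

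**The case against.** The strongest reply is that control timing is not free. Sections 8.1.3 and 16.4 and Appendix 7 all keep repeat samples at or around cycle 3 or 4, and 16.4 prefers draws at routine chemotherapy blood tests. The footnote can be read as releasing controls only from diet days. Section 2.2 gives neither a size nor a time course for the steroid effect, concerns insulin resistance rather than the proteome, and does not show that a few days around a cycle matter. Some of this stands: bias is a possibility, not an established result. It does not dispose of the point, because 8.1.3 still fixes no day relative to the dose for controls, and it contradicts Appendix 5.

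Part of the information needed for adjustment is already collected. Changes in concomitant medication are noted at day 1 of each cycle, and altered cycle dates are documented (section 17). But 8.1.3 promises only menstrual-cycle day alongside these samples, not time since the last chemotherapy or steroid dose.

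Three stronger readings are tempting and not supported:

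- A reader might infer that late baselines also confound the arms. They do not. The sample precedes the interventions and, on the recruiting-hospital route, randomisation itself (section 6.5). Time since first dose is not a minimisation factor, so chance imbalance is possible, but not systematic bias.
- A reader might take 9–33% as an estimate. It is a one-directional illustration in which every control is affected.
- A reader might suppose that Appendix 5 already places the chemotherapy-day sample before premedication. It says nothing on premedication.

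**Conclusion.** The point holds as two limited defects. First, section 8.1.3 as written permits arm-dependent sampling relative to the chemotherapy dose and conflicts with Appendix 5, so the between-arm change in HOMA and proteome can be biased. The direction is unknown. Under the assumed 10–50% shifts the spurious HOMA difference is 9–33% with all controls affected and about 5–18% with half affected, and a shift the other way would mask a true effect. The limits in 16.4 and Appendix 7 reduce this without removing it.

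Second, the pre-chemotherapy baseline in 8.1.3 and 2.6 cannot be squared with Day 15 entry. The consequences are added noise, biased within-arm change (exploratory objectives 2b and 2c) and a contaminated baseline predictor (1a and 1b), not confounding between arms.

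Primary PFS and its event target are unaffected.

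**What to change.** 1. Delete the footnote sentence in section 8.1.3 that leaves control timing open. Take control samples on the Appendix 5 days, two days before and on the day of the same cycle, with the chemotherapy-day sample drawn at the same point relative to treatment in both arms.
2. For every sample, record date, time, and the last chemotherapy and steroid dose.
3. Reconcile the baseline definition with Day 15 entry. Flag samples drawn after the first chemotherapy dose, and adjust for or exclude them in a sensitivity analysis of both the change and the baseline-predictor analyses.

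The cost is a wording change, a few extra data fields, and slightly less scheduling convenience for control participants. The number of samples does not change.

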8.2 Additional measures

8.2.1 Patient demographics

The following demographic health characteristics and body size of the two groups will be collected at baseline:

- General information: age, ethnicity, language spoken and religion (e.g. fasting and Ramadan etc), marital status, number of children living at home, employment status.
- Index of multiple deprivation score (based on post code) (91), highest level of education
- Details of breast cancer diagnosis and previous treatment
- Family history of breast cancer
- Personal weight history: timing of weight gain before or after diagnosis of breast cancer, ever advised to lose weight by a health care professional, ever referred to a weight management service by a health care professional, and recent attempts to lose weight
- Weight, height and BMI assessed in the recruiting centres or at MFT
- Body fat (bioelectrical impedance, Tanita 180), waist, hip measurements in subjects who attend MFT for their baseline appointment

8.2.2 Menstrual cycle

Pre-menopausal women in both diet groups ($\sim 10-20\%$ of the cohort) will be asked to complete a diary sheet of their menstrual cycle throughout the study. This will inform whether women are experiencing chemotherapy associated ammenorhea, which can be a factor in chemotherapy associated weight gain.

8.2.3 Sub-study 2: Qualitative evaluation of the weight loss / lifestyle programme in the energy restriction and resistance exercise only groups.

We are proposing to include a small in depth qualitative study amongst a sub set of participants to assess the acceptability of the intervention and IER diet amongst women with metastatic breast cancer. This sub study will be submitted as a future application to ethics.

9. Criteria for discontinuation of participants in the trial

The energy restriction and exercise interventions will extend until the first disease progression after commencement of study chemotherapy, even if chemotherapy had been stopped due to toxicity or completion of planned treatment (unless excluded by progression of bone metastases, see section 7.3.5). The average chemotherapy period of treatment is projected to be 5.4 months. The longest treatment period is predicted to be two years. We plan to censor patients in the study once the final recruited patient has been in the trial for 12 months.

Ongoing assessment of CT scans as per frequency described in section 8.1.1 (reported back within 21 days) will inform us if patients are experiencing reductions in lean body mass and developing sarcopenia. Sarcopenia is defined using the cut off point for lumbar skeletal muscle index of <38.5 $\rm cm^2/m^2$ for women (96). In the unlikely event that this occur the B-AHEAD 3 dietitian and physiotherapist will review the patient's advice and progress and provide appropriate diet and exercise advice to prevent further reductions. If this advice requires patients to stop following the diet their data will still be used in the primary analysis which is on an Intent To Treat (ITT) basis.

10. Statistical Considerations

10.1 Sample size and power calculations

The sample size was calculated for a phase II screening design, based on a primary outcome of progression free survival, with a time-to-event hazard ratio of 0.65, and with 90% power and a one-sided significance of 20%. Assuming that the estimated PFS in the control arm is 5.4 months, and that we will have a 15 month accrual period and a 15 month follow-up, then a total of 98 events will be required overall. This corresponds to 114 patients required in all, allowing for a 15% drop out we will need to recruit 134 patients overall. The sample size is for a randomised phase II screening design where a randomised phase III is planned in the future. This approach is approved by the Cancer Research UK trials organisation (CTAAC) (73).

10.2 Method of analysis

Assessment of progression-free survival between the two groups will be carried out using Coxproportional hazards regression with appropriate adjustment for competing risks if required.

A comparison of secondary outcomes (toxicity, neuropathy, changes in fat and lean body mass, QOL and muscle strength) between the two groups measured at multiple time points during the study period will be made using regression modelling which takes account of the correlated structure of the data. Generalised estimating equations will be used (with either a binary or normally distributed response as appropriate) with an auto-regressive correlation structure.

11. Finance

The trial is funded by a grant from Anticancer Fund (A Belgian private foundation) www.anticancerfund.org.

12. Publication and dissemination

We will aim to publish this feasibility study in a peer reviewed cancer journal. The findings of this feasibility study will inform the design of a planned Health Technology Assessment (HTA) application for a large scale RCT testing the benefits of energy restriction amongst metastatic breast cancer patients We will inform all study participants that they can request the results of the study.

13. Timelines and milestones

4 month set up locally and within participating centres in the Greater Manchester area and develop resources

15 month for recruitment

12 months for follow up

2 months write up and dissemination

14. Trial Governance

